**6.1.4 End of Treatment visit (Week 24)**

Any unused study drug will be collected.

After 24 weeks of treatment, all subjects will undergo sampling biopsy/biopsies. If residual histologic disease is detected, surgical excision will be performed within 4 weeks of last dose of study drug. If no histologic evidence of disease is observed, subjects will enter the observation period and be followed clinically every 3 months up to one year. (See Appendix 5, Figure 1 and Figure 2.)

Biopsies at Week 24 visit will be performed in similar manner as performed at the Week 12 visit.

For lesions that the investigator has determined to show complete clinical response at Week 24 visit, sampling biopsy will be performed at the farthest edge(s) of pre-biopsy lesion compared to location of initial punch biopsy/biopsies at Pre-study Screening Visit and sites of biopsies performed at Week 24 visit (See Figure 3). Up to three 2-mm or three 3-mm punch biopsies will be performed on the area of tumor clearance at Week 24 when possible. Tumor biopsies may comprise no more than 10% of visible lesion seen at screening visit.

[figure not shown]

Figure 3. Site of biopsies for tumors displaying clinical complete response at Week 24 visit.

For lesions that display partial clinical response or stable disease by clinical response evaluation, “Residual Tumor Assessment” and “Area of Tumor Clearance Assessment” will be performed (See Figure 4)

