#### 6.1.6 Surgery visit

Subjects that are found to have histologic evidence of disease on biopsies performed at Week 24 visit will undergo surgical excision. This visit should be scheduled to occur with 4 weeks of last dose of study drug and will be performed as standard of care treatment.

For lesions that display clinical partial response or stable disease and that show histologic evidence of disease on sampling biopsy at Week 24 visit, residual visible or palpable tumor of target lesion will be removed using the standard Slow Mohs micrographic surgery, margin-controlled excision with rush permanent sections. Two types of specimens will be surgically removed at the time of surgical excision. First, the area of known BCC will be excised and will include the pre-biopsy area. This specimen will be labeled the tumor “debulking” specimen.

Second, marginal tissue will be excised in an attempt to completely remove the tumor until clear surgical margins are obtained, providing the patient the known standard of care. This tissue will be labeled “tumor margins” specimen. Peripheral and deep margins will be examined and recorded if positive or negative. If either peripheral or deep margins is positive, additional surgical excisions will be done in the Mohs tissue orientation fashion until no tumor cells are observed and surgical margins are deemed negative, as is standard of care. In the event that only superficial BCC (sBCC) remains at the surgical margin, it will be at the discretion of the managing physician if further surgery, an alternative treatment modality, or observation will occur.

For lesions that were deemed by investigator to exhibit complete clinical response at week 24 visit, but were found to have residual disease on the sampling biopsy at week 24 visit, the debulking specimen will include area of known BCC as seen on histology.

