## 9.2 SUBJECT SUB-GROUP ASSIGNMENT

A total of 36 subjects with infiltrative/morpheaform, nodular, or superficial BCC will be enrolled in the study. For patients with multiple BCC lesions, one “target lesion” will be identified and used for subject sub-group assignment for the purposes of enrollment and followed for primary endpoint analysis. For scientific purposes, data from BCC tumors other than “target lesion” will also be collected. The lesion(s) biopsied at Screening Visit will be reviewed and each subject will be assigned to a subtype group as detailed below and in Figure 5.

**Step 1.** Infiltrative/morpheaform subtype lesion will be given priority in subject sub-group assignment.

**Step 2.** If a potential subject does not have a possible target lesion that is infiltrative/morpheaform subtype and has a superficial BCC, then the subject will be assigned to the superficial BCC subtype group.

**Step 3.** If no infiltrative/morpheaform BCC or superficial BCC are identified, then nodular BCC will be eligible for enrollment.

[figure not shown]

Figure 5. Target Lesion Assignment Algorithm

If there are two lesions that may be eligible for target lesion assignment based on histologic subtype, then the lesion with larger clinical dimensions will be designated the “target lesion”. See Appendix 10, Target Lesion Assignment Examples for more information.

This “Target Lesion Assignment Algorithm” will continue in this fashion until any two of the subtype groups reaches 26. This is to ensure that each subgroup has at least 10 subjects. At this point, subjects enrolled must have at least 1 BCC of the remaining subtype group.

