#### 9.3.1.1 Clinical Response

- Comparison of number of target lesions in each of the following groups:
  - Complete response, partial response, stable disease, or disease progression as defined above

- Overall response rate and best overall response rate
- Comparison of maximum diameter and lesion area of target lesion(s) post-biopsy and at End of Treatment visit
- Comparison of dimensions of tumor within “debulking” specimen at surgery visit with dimensions of pre-biopsy tumor

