#### 9.3.3 **Efficacy Analysis**

##### 9.3.3.1 **Analysis of Primary Endpoints**

#### 9.3.3.1.1 **Clinical Response**

Comparison of dimensions of tumor within debulk specimen at surgery visit with dimensions of post-biopsy tumor as drawn on template at screening visit will be assessed by a t-test for independent samples.

Sub-group analyses by histologic subtype will be conducted by demographic factors including: gender, race, and anatomic location of target lesion will also assessed for any independent association with clinical response. Statistical significance was defined by alpha 0.05. All analysis was performed using SPSS (PASW) version 18.

Analysis of the following subgroups will be performed:

- Nonaggressive subtypes vs. Aggressive subtypes
- Clinical subtypes (infiltrative/morpheaform, nodular, and superficial)

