#### 9.3.3.1.2 **Histologic response**

Chi-square analysis will be performed to assess histologic response of residual tumor and area of tumor clearance for all tumors and by histologic subtype.

Comparison of the “invasion index” on biopsy specimen and excision specimen will be assessed by a t-test for independent samples.

Histologic subtypes observed on biopsy specimen and excision specimen will be depicted in a frequency table and proportions of each histologic subtype will be compared using a t-test for dependent samples.

Size estimate of tumor based on biopsy specimen to actual size of tumor specimen on day of surgical excision or Mohs surgery will be assessed by a t-test for independent samples.

Location and depth of specific tumor cells of each histological subtype on biopsy and surgical specimen.

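### Three before-and-after comparisons on the same target lesion are planned as independent-samples t-tests and should be paired

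*Combined protocol and SAP*

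**What the plan says.** Section 9.3.3.1 (Analysis of Primary Endpoints) contains three comparisons of an earlier with a later measurement:

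1. Tumor dimensions in the debulking specimen against the post-biopsy dimensions "as drawn on template at screening visit will be assessed by a t-test for independent samples" (9.3.3.1.1).
2. The invasion index "on biopsy specimen and excision specimen will be assessed by a t-test for independent samples" (9.3.3.1.2).
3. A size estimate from the biopsy against the "actual size of tumor specimen on day of surgical excision or Mohs surgery will be assessed by a t-test for independent samples" (9.3.3.1.2).

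For a fourth comparison on the same biopsy and excision specimens, 9.3.3.1.2 says that "proportions of each histologic subtype will be compared using a t-test for dependent samples".

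Other sections show that the measurements belong together. Section 9.2 says that each subject has one target lesion, which is "used for subject sub-group assignment for the purposes of enrollment and followed for primary endpoint analysis". For lesions with partial response or stable disease, Section 6.1.6 says of the debulking specimen that "the area of known BCC will be excised and will include the pre-biopsy area". Section 3 describes one treatment and no control group.

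The baseline for the first comparison is stated in two ways. Section 9.3.1.1 compares the debulking "specimen at surgery visit with dimensions of pre-biopsy tumor"; Section 9.3.3.1.1 uses the post-biopsy tumor.

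**The concern.** An independent-samples t-test is for two separate sets of subjects. Here there is one set, measured twice. The test's standard error leaves out the covariance between the two measurements, so it is correct only when that covariance is zero.

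Lesions that are larger or deeper at screening plausibly tend to stay so. The correlation is then positive, the planned test is conservative, its interval is too wide, and it may miss a real change. If the correlation were negative, the test would reject too often. The documents give no correlation in either direction.

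The independent test also lets unmatched lesions in: up to 36 screening values could be set against a smaller number of surgical values. The difference in means would then no longer be a within-lesion change.

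For the third comparison the question may be how accurately a biopsy estimates size rather than how far the tumor shrank. The values are paired in either case.

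**Working it through.** **The plan's own figures.** No power or standard error is given for these t-tests. The only precision figures are the Section 9.1 response-rate intervals, which reproduce as Wald intervals, p ± 1.96·√(p(1−p)/n):

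- Nodular, 12/16: 0.75 ± 1.96·√(0.1875/16) = 53.8% to 96.2% (stated 54%-96%).
- Other subtypes, 4/10: 0.40 ± 1.96·√(0.24/10) = 9.6% to 70.4% (stated 10%-70%; the 40% is inferred from the midpoint).

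Neither depends on the t-tests.

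**Inputs.** From the documents: alpha 0.05 (9.3.3.1.1; sidedness not stated, two-sided assumed) and 36 subjects (9.1). Assumed: normal data, within-lesion correlation r, ratio s of post-treatment to baseline SD, number of pairs n, and size of change in baseline SDs.

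**Standard error.** With baseline SD 1 and post-treatment SD s:

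- True variance of the mean difference: (1 + s² − 2rs)/n
- Variance used by the independent test: (1 + s²)/n
- Standard error, independent/true: √[(1 + s²)/(1 + s² − 2rs)]

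| r | s = 1 | s = 0.5 |
|---|---|---|
| 0.3 | √(2/1.4) = 1.20 | √(1.25/0.95) = 1.15 |
| 0.5 | √(2/1.0) = 1.41 | √(1.25/0.75) = 1.29 |
| 0.8 | √(2/0.4) = 2.24 | √(1.25/0.45) = 1.67 |

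The ratio is 1 only at r = 0.

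**Type I error by simulation** (20 pairs, s = 1), independent test: 5.0% at r = 0, 2.1% at 0.3, about 0.75% at 0.5, 0.1% at 0.7, and 8.5% at −0.3. The paired test stays at 5.0% throughout. If all 36 screening values were set against 20 surgical values, taken as a random subset, the independent test would have 1.6% at r = 0.5.

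**Power by simulation** (independent t on 2n−2 df, paired t on n−1 df):

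| Pairs | r | s | Change (baseline SD) | Independent | Paired |
|---|---|---|---|---|---|
| 20 | 0.1 | 1 | 0.5 | 33% | 35% |
| 20 | 0.3 | 1 | 0.5 | 31% | 43% |
| 20 | 0.5 | 1 | 0.5 | 29% | 56% |
| 20 | 0.8 | 1 | 0.5 | 22% | 92% |
| 20 | 0.5 | 1 | 1.0 | 94% | 99% |
| 10 | 0.5 | 1 | 0.5 | 12% | 29% |
| 10 | 0.5 | 1 | 1.0 | 59% | 80% |
| 20 | 0.5 | 0.5 | 0.5 | 50% | 69% |

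The paired figures at r = 0.5 and s = 1 agree with the exact noncentral t: 0.565 and 0.989 with 20 pairs, 0.293 and 0.803 with 10.

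**The case against.** The strongest reply is that little depends on these tests. The primary objective in Section 2.1 is to compare subtypes, and these are overall before-and-after comparisons. The study calls itself a pilot and is sized on response rates. With positive correlation, the plausible direction, the planned test is conservative and cannot create a false claim of efficacy. The illustrated loss rests wholly on assumptions: it nearly disappears at r = 0.1 (33% against 35%) and is small for a large change. All of this stands and limits the weight of the point. It does not make the test right. The comparisons sit under the primary endpoint analysis with a formal alpha, and a conservative test still misreports precision when pairs are few.

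Two narrower points also stand:

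- The statement that the debulking specimen includes the pre-biopsy area covers only lesions with partial response or stable disease. For complete clinical responders with a positive Week 24 biopsy, Section 6.1.6 defines the specimen by the area of tumor known from histology. The lesion is still the same one, so the pairing holds, but the two specimen definitions are not identical.
- Section 6.3.2 describes depth, subtype and cellular density from the biopsies, but no overall size estimate. Naming the right test does not define that quantity.

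The baseline conflict and the selection into surgery are separate matters. They belong in the repair because a paired difference needs a single baseline and a stated set of lesions.

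**Conclusion.** The concern holds. Three comparisons of paired data are assigned an unpaired test, while a fourth from the same specimens is assigned a paired one, with no reason given and no correction elsewhere. That the standard error is wrong at any nonzero correlation follows from the variance formula and needs no assumption about the trial.

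The size is a range. At r = 0.5 the standard error is overstated by a factor of 1.41 with equal variances, or 1.29 if the post-treatment SD is half the baseline SD. The power loss then runs from 27 percentage points (20 pairs, 0.5 SD change, equal variances) to about 5 points (20 pairs, 1.0 SD change). The false-positive excess at negative correlation is a theoretical bound on direction, since nothing in the documents suggests a negative correlation.

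This should be corrected before analysis. It does not alter the response categories, the chi-square analysis or the sample-size intervals.

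**What to change.** In Sections 9.3.3.1.1 and 9.3.3.1.2, replace the independent-samples test in all three comparisons with a paired t-test on the within-lesion difference, with the Wilcoxon signed-rank test as a check. In the same edit:

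- **Scale.** Name the one measurement tested in each comparison and use the absolute difference (mm, or mm² for area). This stays defined when the debulking specimen holds no tumor; a log scale does not.
- **Baseline.** Choose pre-biopsy or post-biopsy dimensions and state the same choice in 9.3.1.1 and 9.3.3.1.1.
- **Third comparison.** Define the biopsy-based size estimate.
- **Reporting.** Give the mean paired difference with its 95% confidence interval overall and, descriptively, by subtype, with the number of pairs in each.
- **Lesions covered.** State that the estimates apply only to lesions that reached surgery. Section 6.1.4 says: "If no histologic evidence of disease is observed, subjects will enter the observation period"; Section 6.1.2 (Interval Visits) has the same route at Week 12 for complete clinical responders. Pairing does not remove that selection. Note also the two definitions of the debulking specimen.

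The cost is rewording three sentences in two subsections, short decisions on baseline, scale and the size estimate, and a few lines on reporting and on which lesions are analyzed. No new data are needed and study conduct does not change, provided this is done before analysis.

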#### 9.3.3.1.2 **Histologic response**

Chi-square analysis will be performed to assess histologic response of residual tumor and area of tumor clearance for all tumors and by histologic subtype.

Comparison of the “invasion index” on biopsy specimen and excision specimen will be assessed by a t-test for independent samples.

Histologic subtypes observed on biopsy specimen and excision specimen will be depicted in a frequency table and proportions of each histologic subtype will be compared using a t-test for dependent samples.

Size estimate of tumor based on biopsy specimen to actual size of tumor specimen on day of surgical excision or Mohs surgery will be assessed by a t-test for independent samples.

Location and depth of specific tumor cells of each histological subtype on biopsy and surgical specimen.

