## 2. STUDY OBJECTIVES

### 2.1 PRIMARY OBJECTIVES

- To compare the efficacy of vismodegib in various histologic subtypes of high risk and/or locally advanced basal cell skin cancer

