At week 12, Intra-treatment tissue histopathologic evaluation will be performed to assess histologic response. For subjects with apparent clinical complete response at Week 12 and no histologic evidence of disease is observed, subjects will enter the observation period and be followed clinically every 3 months up to one year (See Appendix 5, Figure 3 for more

information). Sample diagrams demonstrating the sites of screening biopsies and Week 12 biopsies for a tumor is seen in Section 6.1.3.

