#### **Tumors Exhibiting Complete Clinical Response**

For lesions that the investigator has determined to show complete clinical response at Week 12 visit, sampling biopsy will be performed at the farthest edge(s) of pre-biopsy lesion compared to location of initial punch biopsy/biopsies at Pre-study Screening Visit (See Figure 1 A). Up to three 2-mm or three 3-mm punch biopsies will be performed on the area of tumor clearance at Week 12 when possible. Tumor biopsies may comprise no more than 10% of visible lesion seen at screening visit.

[figure not shown]

Figure 1. Site of Week 12 biopsies for tumors with exhibiting complete clinical response.

For lesions that display partial clinical response or stable disease by clinical response evaluation, “Residual Tumor Assessment” and “Area of Tumor Clearance Assessment” will be performed (See Figure 2.).

[figure not shown]

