### 6.2.2 Clinical response evaluation of target lesion

Measurements of longest length and perpendicular diameter of target lesion(s) will be recorded at each interval visit and compared template map drawn treatment initiation visit.

**Complete response** will be defined as the disappearance of a palpable or visible tumor.

**Partial response** will be defined as a reduction of more than 50% in the diameter of a palpable or visible tumor.

**Stable disease** will be defined as no change in diameter of palpable or visible tumor or a reduction of up to 50% in the diameter of a palpable or visible tumor.

**Disease progression** will be defined as increase of 20% in either perpendicular diameter of a palpable or visible tumor.

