#### 9.3.1.2 **Histologic response (at Week 12 and Week 24/Surgical Visit)**

- **Residual tumor**
  - Evidence of any histologic change in residual tumor tissue compared to pre-treatment biopsy specimens
  - Estimate of changes in cellular density and composition at Week 12 and Week 24/Surgical Visit
- **Area of Tumor Clearance**
  - Assessment of histologic clearance in areas of apparent clinical tumor clearance at Week 12 and Week 24, and/or Surgical Visit
- Comparison of deepest “invasion index” on biopsy specimen, at Week 12 biopsy, and “debulking” specimen or “tumor margins” specimen” at Surgery visit
- Histologic subtypes observed on pathologic specimens (Screening visit and Week 12 and Surgical excision specimen) Location and depth of specific tumor cells of each histologic subtype on biopsy, week 12 biopsy, and Surgical excision specimens
- Percentage of each histologic subtype in tumor specimen on biopsy, Week 12 biopsy and surgical excision specimens

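### The two histologic-response tables take their denominators from clinical response, so neither compares subtypes on all treated lesions

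*Combined protocol and SAP*

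**What the plan says.** The primary objective (2.1) is comparative: "To compare the efficacy of vismodegib in various histologic subtypes of high risk and/or locally advanced basal cell skin cancer". Histologic response is part of the primary endpoint, and 9.3.1.2 gives it separate components. For residual tumor the outcome is "Evidence of any histologic change in residual tumor tissue compared to pre-treatment biopsy specimens", together with changes in cellular density and composition. For the cleared area it is "Assessment of histologic clearance in areas of apparent clinical tumor clearance at Week 12 and Week 24, and/or Surgical Visit". The planned analysis (9.3.3.1.2) is "Chi-square analysis will be performed to assess histologic response of residual tumor and area of tumor clearance for all tumors and by histologic subtype". No denominator, combined per-lesion outcome or rule for an absent specimen is given.

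The biopsy rules in 6.1.3 and 6.1.4 decide which specimens exist. Residual-tumor and cleared-area sampling are both prescribed "For lesions that display partial clinical response or stable disease by clinical response evaluation". Lesions with complete clinical response are punched only in the cleared area. Cleared-area punches are taken where feasible. In 6.2.2, complete response "will be defined as the disappearance of a palpable or visible tumor", and stable disease "will be defined as no change in diameter of palpable or visible tumor or a reduction of up to 50% in the diameter".

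On early exit, 6.1.2 (Interval Visits) says: "For subjects with apparent clinical complete response at Week 12 and no histologic evidence of disease is observed, subjects will enter the observation period". Section 3 uses complete histologic response to decide entry to observation, but Section 9 never analyzes it as a per-lesion outcome.

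**The concern.** Clinical response is itself an effect of treatment. If clinical response decides whether a lesion has the specimen a table needs, the table compares subtypes within groups selected on outcome. The residual-tumor table leaves out the lesions that cleared clinically, and the cleared-area table leaves out those that did not shrink. A real subtype difference in overall histologic response could be shrunk, hidden or reversed in either table, in the part of the primary endpoint meant to answer the trial's main question.

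**Working it through.** **1. The plan's own figures.** The plan gives no histologic rate. Its nearest figures are the intervals in 9.1, which are Wald intervals, p ± 1.96√(p(1−p)/n):
- n = 16, p = 0.75: 0.75 ± 1.96 × 0.108 = 53.8% to 96.2% (stated 54%-96%).
- n = 10, p = 0.40 (the midpoint implied; the rate is not stated): 0.40 ± 1.96 × 0.155 = 9.6% to 70.4% (stated 10%-70%).

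Both reproduce, and both use the whole subtype group as denominator. The histologic tables would not.

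**2. Which specimen exists for which lesion** (6.1.3 to 6.1.8, 6.2.2, Appendix 6).

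| Target lesion | Residual-tumor punch | Cleared-area punch | Later tissue |
|---|---|---|---|
| Complete response, histologically clear, stops at Week 12 | None | Week 12 | None scheduled; biopsy only for a suspected recurrence or new lesion |
| Complete response at Week 24 | None | Week 24, where feasible | Debulking specimen if the Week 24 biopsy is positive |
| Partial response, or stable with some shrinkage | Yes | Where feasible | Excision if the Week 24 biopsy is positive |
| Stable, no shrinkage | Yes | None: no cleared area | Excision if the Week 24 biopsy is positive |
| Progression | Type not stated; early termination follows Week 24 procedures | Not stated | Excision if the biopsy is positive |

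**3. Worked counts (assumed).** Subtype A, n = 10: 6 complete responders, all histologically clear, and 4 with residual tumor, of which 1 responds. Subtype B, n = 16: 2 complete responders, both clear, and 14 with residual tumor, of which 6 respond.
- All lesions: A (6+1)/10 = 70%; B (2+6)/16 = 50%.
- Residual tumor only: A 1/4 = 25%; B 6/14 = 43%.
- Cleared area only, further assuming 8 of B's lesions have no cleared area, with 8/10 clear in A and 8/8 in B: A 80%; B 100%.

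Both specimen tables reverse the order, the first because A's best lesions are absent and the second because B's worst are. The result is fragile: with one more residual-tumor responder in A it is 2/4 = 50% against 43%, and the residual-tumor reversal is gone.

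Smallest expected cell counts: residual table 4 × 7/18 = 1.6; cleared-area table 8 × 2/18 = 0.9; all-lesion table 10 × 11/26 = 4.2. All are small for a chi-square test.

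**4. Assumed response mixes.** Mixes and histologic rates are listed as complete/partial/stable, with 200,000 simulated trials per scenario, n = 10 (A) against 16 (B). B's mix is 20/40/40% throughout.

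| Scenario | All lesions, A v B | Residual only, A v B | Residual order reversed when A leads on all lesions |
|---|---|---|---|
| 1. A mix 60/30/10%; rates A 90/20/0%, B 90/40/20% | 60% v 42% | 15% v 30% | 69% |
| 2. A mix 60/30/10%; rates 90/30/0% in both | 63% v 30% | 22.5% v 15% | 38% |
| 3. A mix 60/20/20%; rates 90/30/0% in both | 60% v 30% | 15% v 15% | 51% |

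For scenario 1, subtype A: all lesions 0.6×0.9 + 0.3×0.2 + 0.1×0 = 0.60; residual only (0.3×0.2 + 0.1×0)/0.4 = 0.15. The mean residual-tumor denominators are 10 × 0.4 = 4.0 and 16 × 0.8 = 12.8.

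Scenario 1 is a systematic reversal. In scenarios 2 and 3 the expected residual-tumor difference shrinks from 33 to 7.5 points and from 30 to 0, and the reversals are small-sample noise. With cleared-area clearance rates assumed at 80% to 90%, the expected cleared-area comparison is 87% v 90% in scenario 1 and 90% v 90% in the other two.

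**5. Week 12 stoppers (assumed).** If 3 of 10 clear and stop at Week 12 and 3 more clear by Week 24, a table of Week 24 specimens shows 3/7 = 43%; counting all ten gives 6/10 = 60%.

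**The case against.** A reader might infer that the best responders drop out of the histologic analysis and that the subtype ranking will reverse. The documents do not support that. Complete clinical responders are punched in the cleared area at Week 12, and at Week 24 if still on treatment. Under 6.1.6 they also have a debulking specimen if the Week 24 biopsy is positive. They are missing only from the residual-tumor punches and, after a Week 12 exit, from scheduled Week 24 tissue.

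Further points stand:
- The residual-tumor endpoint is any histologic change, not clearance, so the worked counts use a stand-in outcome. The denominators are the same whichever outcome is used.
- Reversal depends on chosen counts. No general bias against the more responsive subtype is shown.
- That the two specimens are analyzed separately is the natural reading of 9.3.1.2, not its words. If one combined outcome was meant, it is undefined and needs the same edit.
- Leaving Week 12 stoppers out of Week 24 is an inference; the plan has no rule either way.
- The clinical categories in 9.3.1.1 need no tissue and cover every target lesion, and 9.1 calls the study a pilot. However, the only test that 9.3.3.1.1 names is a t-test using debulking dimensions, which themselves exist only after surgery.

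Asking for the analysis to cover all tumors does not answer the point, because the missing specimens were never taken.

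**Conclusion.** The point holds in limited form. As written, 9.3.1.2 and 9.3.3.1.2 compare subtypes on lesions selected by a post-treatment outcome, with no all-lesion denominator and no per-lesion histologic response. That part follows from the biopsy rules without any assumption. The size and direction of the distortion do not: they depend on clinical response mixes and histologic rates by subtype, which the documents do not give. Under the assumed scenarios, a true all-lesion difference of 18 to 33 points became anything from 7.5 points in the same direction to 15 points in the opposite direction in the residual-tumor table. A reversed ranking is possible but is not shown.

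**What to change.** In 9.3.1.2 and 9.3.3.1.2:
- Define one binary histologic response per target lesion and visit, matching the plan's own complete histologic response: no tumor on any specimen taken at that visit, from residual or cleared area.
- Use all treated target lesions in the subtype as denominator, one per subject as assigned under 9.2.
- For Week 24, carry forward the Week 12 result for subjects who stopped at Week 12 with complete clinical and histologic response.
- Count other lesions without an evaluable specimen as non-responders, with a sensitivity analysis on evaluable lesions only.
- Compare subtypes with an exact test, since groups are 10 to 16.
- Keep the residual-tumor and cleared-area findings as descriptive tables, split by clinical response. Punches cover at most 10% of the lesion, so a lesion still visible but negative on biopsy should be identifiable.

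Two inconsistencies must be reconciled first. Section 6.1.4 requires a Week 24 biopsy that the Appendix 6 flowcharts do not show. Section 6.6.2 has every treated subject complete the excision, whereas 6.1.4 sends those without histologic disease to observation.

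Cost: wording only, with no samples beyond those that 6.1.3 and 6.1.4 already require. Non-responder counting is slightly conservative if few lesions go unsampled. It could fall on complete responders who could not be punched, which is why the sensitivity analysis is needed.
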